2.0. Background/Rationale

Family planning decisions are increasingly important for women with CF as most reach reproductive age in reasonable health. As CF care management and directed therapies advance, the number of women with CF in the US over age 18 has nearly doubled over the last 15 years: from 4,000 to 7,200. The CFF has an existing comprehensive patient registry, the CFFPR, which captures annual data on over 90% of all persons with CF in the US (1). While it is comprehensive regarding most aspects of CF patients' health, the CFFPR currently only asks one question that addresses reproductive health for women over 18 living with CF: "Was the patient pregnant during the reporting year?".

Reliable information is urgently needed to enable healthcare providers to help CF women understand the effectiveness and safety of current contraceptive methods for them. While infertility usually affects men with CF, at least 50% of women with CF are estimated to be physiologically capable of becoming pregnant without fertility treatment (2); however, that percentage is expected to rise with the use of new life sustaining medications, such as the CFTR modulators and especially the newly Food and Drug Administration (FDA)-approved triple-combination modulator, TRIKAFTA® (3).

Our recently completed survey study among 150 women at three CF centers, suggests that only about 60% of reproductive—aged women with CF are using contraception (4). Among those who are, oral contraceptive pills (OCPs) and condoms are the most commonly reported methods. Gaps in quality contraceptive care for women with CF exist, in part because, surprisingly, women with CF prefer to receive their sexual health care within the CF clinics, but many CF providers do not feel prepared to deliver safe and detailed contraception care (5). This information gap is exacerbated by the limited data which exist to inform contraceptive care provision for women with CF. In fact, most studies evaluating contraceptive safety are limited to oral contraceptive pills, even though the number of choices of FDA-

CASE.4.CF Study Protocol

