7.1. Study Setting

We intend to enroll up to 625 women, aged 18-45 years, at 10 separate CF centers. We may over-enroll the sample by 25 women to account for women who may have participated in the prior contraceptive study in 2017. This will allow us to perform a sensitivity analysis excluding women who participated in the pre-study, while maintaining study power.

Name of Institution	Institution PI(s)	Number of women with CF aged 18-45 years
University of Washington	[name], MPH	141
	[name]	
University of Texas Southwestern	[name], MS	140
National Jewish Hospital	[name], MS	233
University of California San Diego	[name]	120
	[name], MPH	
University of Pittsburgh	[name], MS	106
University of Pennsylvania	[name]	128
	[name], MPH	
John's Hopkins University	[name], MPH	159
University of Alabama	[name]	135
	[name]	
	[name] RN	

Name of Institution	Institution PI(s)	Number of women with	
		CF aged 18-45 years	
Harvard U/Boston	[name]	189	
Mount Sinai	[name]	51	

We anticipate that each site will be able to enroll 50% of eligible women ages 18-45 years into the study. We have chosen the lower age range because of estimated age of sexual debut among young women with CF is between ages 16-17 years (5) and it is expected that some women aged 18 will have started using contraception. We have chosen the upper age range of 45 years because of the lower life expectancy of women with CF compared to the general population and inherent bias that adults with CF who live past the currently life expectancy are most likely healthier than younger adults with CF (10).

Table 3: Age distribution goals for study enrollment

Age Distribution of Women with CF		
Age Range (years)	Approximate number of subjects planned	
18-35	383	
36-45	192	

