7.5. Outcomes (include DAG diagrams to show relationships between exposure and outcomes)

Table 5: Outcomes and associated confounders and covariates

Exposure of interest	Outcome	Confounders/Covariates	Rationale
Combined	Pulmonary outcomes	Smoking	Affects lung function
hormonal contraception (CHC)	 Annual pulmonary exacerbation rate (PEx) (defined as episodes requiring intravenous 	Insurance status (reflection of SES)	Will be used as socioeconomic indicator. Less access to meds may mean less
&	antibiotic use at home or in		compliance
Progestin-only	hospital)Absolute change in FEV1 (in	Age	Lung function worsens as one ages
contraception	liters) Prevalence of micro-organism (defined as 1 or greater sputum	Education (reflection of SES)	Affects contraceptive knowledge decision making
	culture within a 12-month period)P. aeruginosa	ВМІ	Associated with better or worse health status in general

Exposure of interest	Outcome	Confounders/Covariates	Rationale
	 MDR P. aeruginosa Staph aureus 	Exercise	May reduce pulmonary exacerbation rates
	MSSA MRSA	CF genotype class	Associated with severity of disease
	Secondary infections: • Burkholderia cepacia	CFTR modulator treatment	Likely preserves pulmonary decline
	 Burkholderia cenocepacia Mycobacterial species –includes M. tuberculosis and NTM species 	Comorbidity with CFRD (defined as requiring chronic insulin therapy) (11)	Associated with worse disease (reduced immunity)
		Length of hormonal contraceptive use (person-year of exposure)	
	Venous/arterial thromboembolism (VTE)	BMI ≥ 30	
	 Noted on self-respondent survey (defined as blood clot requiring anticoagulation treatment) 	Age > 35 years PMHx for thrombophilia Arterial/venous lines or ports Pmhx cancer Smoking	
	Liver outcomes	BMI	Obesity contributes to
	 Liver disease, non-cirrhosis Gallstone, requiring surgery/procedure (defined as present or absent as 	Comorbidity with diabetes	liver dysfunction Associated with worse disease (reduced immunity)
	recorded in CFFPR)	Hepatitis	Risk factor for liver dysfunction
		CF genotype class Length of hormonal contraceptive use (person-year of exposure)	
	 Serum ALT, GGT (meets criteria if hepatic transaminases and GGT levels exceed upper limit of normal on at least 3 consecutive occasions over 12-month period) (12) 		Will track meeting criteria annually over time
	CF-related diabetes		
	 Serum ogtt trends New onset insulin resistance or diabetes (defined as 		

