9.3. Statistical Methods

Because this is a retrospective cohort study, we are most interested in determining whether this exposure (to hormonal contraception) is associated with our primary outcome (counting the number of pulmonary exacerbations requiring additional IV in a given year) and/or our secondary outcomes (new respiratory microbiology, liver disease/non-cirrhosis, gallstone, requiring surgery/procedure, improved BMI, incidence of VTE, osteoporosis and fragile bone fracture). Women on hormonal contraception will be compared to the primary control group of women on non-hormonal contraception. We will also compare to women on no contraception, as the secondary control group. We will exclude persons with these existing diagnosis at the start of the follow up period for outcome data (January 1, 2010). Within this objective we will be able to calculate incidence rates, relative risks and confidence intervals. We will use Poisson regression to calculate progestin-only and combined hormonal method to non-hormonal method pulmonary exacerbation rate ratios and 95% confidence intervals. This allows for adjustment of follow-up time of each individual.

(Objective 1a): We will evaluate lab values over time (ppFEV1%, serum AST, ALT, alkaline phosphatase) to determine if trends between hormonal contraceptive users and non-hormonal contraceptive users differ. See Table 5 for confounders and covariates that we will use to adjust for the primary and secondary outcomes.

We will model ppFEV1 via generalized estimating equations (GEE), allowing for correlation within a subject, and compare via a fixed effect for exposure. Among women who change or stop contraception, we will estimate and compare within-participant difference in outcomes via the model (if numbers allow). We will censor women who switch method types or become pregnant, and for 6 months post pregnancy, for the primary analysis and subsequently follow them to leverage within-patient data and analyze changes in pulmonary status and contraception. Presence of respiratory microbiology will be estimated longitudinally via GEE with a logit link function. Graphic displays and summary statistics will be used; all *p* values will be two-sided.

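### CF center is not among the planned adjusters, although the primary outcome depends on a decision to give IV antibiotics and women come from 10 centers

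*Combined protocol and SAP*

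**What the plan says.** Section 9.3 of the combined protocol and SAP defines adjustment by reference: "See Table 5 for confounders and covariates that we will use to adjust for the primary and secondary outcomes". For the pulmonary outcomes, Table 5 (Section 7.5) lists smoking, insurance, age, education, BMI, exercise, CF genotype class, CFTR modulator treatment, CF-related diabetes and duration of hormonal use. Center is not listed there or under any other outcome.

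The primary outcome is defined by treatment. Table 5 gives it as "Annual pulmonary exacerbation rate (PEx) (defined as episodes requiring intravenous" antibiotics at home or in hospital, and Section 9.3 as "counting the number of pulmonary exacerbations requiring additional IV in a given year".

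The primary model is stated as: "We will use Poisson regression to calculate progestin-only and combined hormonal method to non-hormonal method pulmonary exacerbation rate ratios". No center term, stratum, random effect or center-level variance is mentioned. For lung function the plan says "We will model ppFEV1 via generalized estimating equations (GEE), allowing for correlation within a subject", which covers repeated measures on one woman but not women sharing a center.

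Section 7.1 sets the recruitment frame: "We intend to enroll up to 625 women, aged 18-45 years, at 10 separate CF centers".

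**The concern.** Two women with the same illness can contribute different counts if one attends a center that moves to IV antibiotics sooner. If such centers also have a higher or lower share of hormonal users, the comparison of hormonal with non-hormonal users picks up center practice along with any effect of the method.

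Section 2.0 makes the exposure link plausible. It reports that "women with CF prefer to receive their sexual health care within the CF clinics" and that many CF providers feel unprepared to give contraceptive care, so the clinic a woman attends may influence her method.

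The primary rate ratio is at stake. The covariates in Table 5 describe patients. Insurance and education may absorb part of a center difference, but they do not stand in for a center's readiness to treat with IV antibiotics.

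**Working it through.** **1. Conditions for confounding.** Center must be related to both the IV-treated exacerbation rate and contraceptive choice. The outcome definition and Section 2.0 make each link plausible. The documents give no figures for either, so everything in steps 2 and 3 rests on assumed values.

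**2. Hand illustration.** Take two equal groups of centers and no true effect. In the high-IV group the rate is k times that of the other group. Hormonal shares are p_H (high-IV group) and p_L, with p_H + p_L = 1. The crude rate ratio is then

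RR = (p_H·k + p_L) / ((1 − p_H)·k + (1 − p_L)).

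- Shares 45% and 55%, k = 1.25: 1.1125 / 1.1375 = 0.98
- Shares 40% and 60%, k = 1.5: 1.2 / 1.3 = 0.92
- Shares 30% and 70%, k = 2: 1.3 / 1.7 = 0.76

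Swapping the shares gives the reciprocals: 1.02, 1.08 and 1.31.

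**3. Simulation over 10 centers.** Sizes are proportional to the site counts in Section 7.1 (141, 140, 233, 120, 106, 128, 159, 135, 189, 51; total 1,402). Assumed: mean hormonal share 0.5, center SD of log rate 0.2 to 0.4, SD of hormonal share 0.10 to 0.15, true RR 1, no covariate adjustment, 20,000 sets per setting. The RR is the exposure-weighted mean rate divided by the control-weighted mean rate.

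| Correlation of center rate with hormonal share | Null RR, mildest to most extreme setting |
|---|---|
| +0.5 | mean 1.04 to 1.12 |
| 0 | 95% range 0.95–1.05, widening to 0.86–1.17 |
| −0.5 | mean 0.97 to 0.90 |

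The 97.5th percentile in the most extreme setting at +0.5 is about 1.35.

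**4. Power cost of adjusting.** Section 7.7 states 80% power for RR 0.70 with 575 enrolled, alpha 0.05 and 15% attrition, at 0.8 exacerbations per year. I assumed a 1:1 split of hormonal to non-hormonal users, one year per woman and no overdispersion.

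- Analysed N = 575 × 0.85 = 488.75, or 244.4 per group
- Expected events: 244.4 × 0.8 × 0.70 = 136.9 and 244.4 × 0.8 = 195.5
- SE of log RR = √(1/136.9 + 1/195.5) = 0.1115
- Power = Φ(0.3567/0.1115 − 1.96) = Φ(1.24) = 0.893

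This does not reproduce the stated 80%. Section 7.7 does not give the person-time or any variance inflation behind its figure, so the gap does not prove an error. The 0.893 serves here only as the reference for the relative loss.

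With center fixed effects, the information is the sum over centers of 1/(1/E1 + 1/E0), where E1 and E0 are the expected events in each group at that center.

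| Hormonal share across centers (assumed) | Information | Power |
|---|---|---|
| 50% in all | 80.5 | 0.893 |
| 40% to 60% | 79.1 | 0.887 |
| 30% to 70% | 75.4 | 0.872 |

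**The case against.** The strongest reply is that the confounding is hypothesised. Section 2.0 describes CF providers in general and does not say that practice differs between centers. The simulated ratios are crude, and some Table 5 covariates may remove part of what they show. This stands, and it limits the claim to plausibility.

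At zero correlation, the widest range (0.86–1.17) is narrower than ordinary Poisson error. For 489 women over one year, the null SE is √(2/195.5) = 0.101, giving 0.82–1.22. This also stands for one year per woman. Outcome follow-up starts on January 1, 2010, however, and more person-time shrinks sampling error without shrinking a center imbalance.

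The plan is not declared final: Sections 6.0 and 7.7 say the analysis will be refined, and the DAGs named in the heading of Section 7.5 are not visible in this text. A reader might infer that Table 5 is a fixed, closed list, and the documents do not go that far. Neither point supplies a center term, though, and Section 9.3 points to Table 5.

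Section 9.3 also plans within-woman comparisons among those who change or stop a method, which would remove stable center differences. That analysis is conditional on numbers and is not the primary one.

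Finally, enrolling center is an imperfect measure. Table 4 requires one visit in the last two years, while outcomes run from 2010 and exposure from 2008. This is a fair limit on the remedy.

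**Conclusion.** The point holds as a gap in the adjustment set that should be closed. The stated models leave out a plausible confounder that is known from recruitment and cheap to include.

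Two stronger readings are not supported. A reader might infer that the primary rate ratio will be biased, or biased upward. Without between-center data neither can be said, and a negative correlation would produce an apparent benefit of the kind hypothesised in Section 3.0 for estrogen-containing methods. A reader might also take 1.35 as a worst case. It is the 97.5th percentile of the most extreme assumed setting, and more extreme values occur.

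On the assumed ranges, the average distortion of a null rate ratio is roughly 4% to 12% upward or 3% to 10% downward, before any covariate adjustment. These figures illustrate scale and do not estimate this study's bias.

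**What to change.** - Add enrolling center to Table 5, and enter it as a fixed effect (9 indicators) in the Poisson model for exacerbations and in the GEE models.
- State that the center identifier is kept from recruitment (Section 7.6.2), because the Appendix list of registry variables does not request one.
- For rare outcomes (thromboembolism, gallstones requiring surgery), omit center from the main model and say so.
- State as a limitation that enrolling center may not be the treating center in earlier years.

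The cost is a change of SAP wording and 9 degrees of freedom among about 489 analysed women. On the assumptions above, power falls from 0.893 to between 0.887 and 0.872 when hormonal share varies across centers. No new data collection is needed.

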3.0. Hypothesis

- Estrogen-containing methods, but not progestin-only methods, reduce the annual rate of pulmonary exacerbations, the microorganisms associated with a more rapid decline in lung function, and improve ppFEV1 (or absolute FEV1) of women with CF when compared to women with CF who use non-hormonal contraception (control group).
- Estrogen-containing oral methods of birth control are associated with higher incidence of gallbladder disease (defined as gallstones, requiring surgery), increased liver function enzyme values, and/or increased incidence of thromboembolism among women with CF.
- Both estrogen-containing and progestin-only hormonal methods improve BMI among women with CF, which is linked to nutritional status.
- The strength of agreement between DXA scan T-scores and CFFPR data about osteoporosis, osteopenia and bone fracture will be "substantial."
- The effectiveness of oral birth control is reduced compared to other methods of hormonal birth control in the presence of CFTR modulator use.
- Hormonal birth control use results in a greater proportion of patients with mucoid *Pseudomonas aeruginosa*, in patients who are *P. aeruginosa* positive, compared to non-hormonal contraceptive users.

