4.2. Secondary Study Objectives/Endpoints

- To assess the association of hormonal contraceptive use on trends in lung function (FEV1) over time, compared to non-hormonal contraceptive users (primary control) and non-contraceptive users (secondary control).
- To assess the association of hormonal contraceptive use on the incidence of venous or arterial thromboembolism.
- To assess the association of hormonal contraceptive use on prevalence of liver dysfunction, defined as gallstones (requiring surgery), hepatic steatosis, hepatic cirrhosis, and/or incidence of increased liver enzyme test values (ALT/GGT). Increased liver enzymes is defined as exceeding upper limit of normal on at least 3 occasions over 12-month period.
- To assess the association of hormonal contraceptive use on serum glucose trends, incidence of insulin resistance or time to CF-related diabetes (requiring insulin treatment).

- To assess association of hormonal contraceptive use on nutritional status through the evaluation of BMI trends.
- To validate bone health information in CFFPR with chart data obtained from one CF center (limited due to need for data use agreements between institutions for EMR data).
- To determine if those using hormonal contraception while using CFTR modulators report higher rates of unintended pregnancy compared to those taking non-hormonal contraception.
- To assess proportion of mucoid *P. aeruginosa*, in patients who are *P. aeruginosa* positive, among hormonal contraception users compared to non-hormonal contraceptive users.

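### The FEV1 objective asks whether trends differ, but the only between-group ppFEV1 contrast named in 9.3 is a fixed effect for exposure, with no time or exposure-by-time term.

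*Combined protocol and SAP*

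**What the plan says.** Section 4.2 sets as its first secondary objective the association of hormonal contraceptive use with "trends in lung function (FEV1) over time, compared to non-hormonal contraceptive users (primary control) and non-contraceptive users (secondary control". Objective 1a in 9.3 repeats the question: ppFEV1 and liver tests are followed over time "to determine if trends between hormonal contraceptive users and non-hormonal contraceptive users differ".

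The next paragraph of 9.3 gives the only ppFEV1 model: "We will model ppFEV1 via generalized estimating equations (GEE), allowing for correlation within a subject, and compare via a fixed effect for exposure". The response is ppFEV1 itself. The paragraph adds one other comparison, limited to a subgroup: "Among women who change or stop contraception, we will estimate and compare within-participant difference in outcomes via the model (if numbers allow".

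Three other places bear on the point:

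- The pulmonary block of Table 5 (section 7.5) gives the FEV1 outcome as "Absolute change in FEV1", in liters. Its covariates include age, CF genotype class, CFTR modulator treatment and "Length of hormonal contraceptive use (person-year of exposure". Section 9.3 says that Table 5 covariates will be used for adjustment.
- Section 3.0 hypothesizes that estrogen-containing methods "improve ppFEV1 (or absolute FEV1) of women with CF", which can be read as a question about level.
- Section 6.0 says that the analysis plan will be refined during the pilot, without saying how.

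**The concern.** A difference in trend is a difference in slopes. A fixed effect for exposure on repeated ppFEV1 values is a difference in mean level over the observed period. The two coincide only in special cases.

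Under section 8.1, women belong to a group through their own choice of contraception, so the groups may well start at different FEV1 levels. A starting gap then enters the exposure coefficient directly. If 9.3 is followed as written, the trend objective could be reported as benefit or harm when annual decline is equal, or as no difference when decline differs. Leaving the contrast open also allows level or slope to be chosen after the registry data have been seen.

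**Working it through.** **Is a slope contrast stated elsewhere?**

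- Age, even if updated over time, gives one common slope for all groups.
- The within-woman comparison covers only women who change or stop a method, and only if numbers allow.
- Absolute change in liters (Table 5) is not the response modelled in 9.3.
- Length of hormonal use is the one candidate. Suppose it is updated over time and counted from zero at the start of follow-up. It is then 0 in non-users and equals elapsed time in users, so next to a common time trend it is exposure x time. The exposure coefficient would then be the gap at zero duration, which is still not a trend. The coding is not stated.

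**What the named coefficient estimates.** Let g = 1 for users and 0 for the comparator. Write mean ppFEV1 at time t as a + d0·g + (b + d1·g)·t, where d0 is the starting gap and d1 the slope difference. With the same observation times in both groups and no exposure-by-time term, the exposure coefficient is d0 + d1 × (mean t). For nine annual values, t = 0 to 8 and mean t = 36/9 = 4 years.

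- d0 = 0, d1 = 0.5: 0 + 0.5 × 4 = 2 points.
- d0 = -2, d1 = 0.5: -2 + 2 = 0 points.
- d0 = 3, d1 = 0: 3 points, with equal decline.

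This step needs no assumed SD.

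**How often the tests would mislead (illustration).** The documents give no FEV1 SDs, gaps or slopes, so those inputs are assumptions.

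- Users: 575 × 0.85 = 489 (section 7.7), half of them hormonal, so 244.
- Comparator: 244 is an upper bound, because it pools both control groups. 49 is a low illustration: 60% using any method (section 2.0) minus 50% hormonal (section 7.7) is 10% of 489.
- SDs: between-woman 14-20, slope 1-2 per year, residual 5-8.
- m annual values per woman, two-sided 0.05.

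With Sxx the sum of squared deviations of t:

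- SE(level) = sqrt[(1/n1 + 1/n2) × (SDb² + (SDslope × mean t)² + SDres²/m)]
- SE(slope) = sqrt[(1/n1 + 1/n2) × (SDslope² + SDres²/Sxx)]

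Example: 244 v 244, SDs 20/1.5/6, nine values, Sxx = 60.

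- SE(level) = sqrt[0.0082 × (400 + 36 + 4)] = 1.90
- SE(slope) = sqrt[0.0082 × (2.25 + 0.60)] = 0.153
- A 0.5/yr difference with equal start gives z = 2/1.90 = 1.05 for level (power 18%) and z = 0.5/0.153 = 3.27 for slope (power 91%).

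Ranges over the assumption grid, as the chance of a significant result:

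| Scenario | Follow-up | Contrast | 244 v 244 | 244 v 49 |
|---|---|---|---|---|
| 3-point gap, equal slopes | 4-8 yr | exposure | 33-64% | 14-27% |
| 3-point gap, equal slopes | 4-8 yr | exposure x time | 5% | 5% |
| Equal start, 0.5/yr | 4-8 yr | exposure | 8-33% | 6-14% |
| Equal start, 0.5/yr | 4-8 yr | exposure x time | 40% to over 99% | 17-77% |
| Equal start, 0.5/yr | 3 yr | exposure x time | 27-62% | 12-26% |
| Equal start, 0.5/yr | 2 yr | exposure x time | 15-32% | 8-14% |

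**Fitted GEE** (exchangeable, robust SEs, 1,000 simulated cohorts, nine annual values, SDs 20/1.5/6, 244 v 244), as exposure then exposure x time:

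- 0.5/yr with users starting 2 points lower: 5.8% and 90.3%.
- 3-point gap, equal slopes: 34.1% and 3.5%.
- No gap, no slope difference: 4.7% and 5.3%.

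**Does exposure x time alone suffice?** Assume that a fixed trait is present in 60% of one group and 40% of the other and adds 1.5 points/yr of decline, with no exposure effect. With the trait as a main effect only, the exposure x time estimate averages -0.30/yr (1.5 × 0.20 in size). It is significant in 44.6% of cohorts (244 v 244) or 20.2% (244 v 49). Adding trait x time returns the estimate to 0.00/yr, with 4.5% and 4.7% significant.

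**The case against.** The strongest reply is that 9.3 is terse rather than wrong. It states the intention to compare trends, Table 5 names a change outcome, and an exposure-by-time term may have been meant. A fixed effect on a change score would be a trend contrast, and rewording the objective as a level difference would also remove the conflict. But 9.3 makes ppFEV1 itself the response and names only the exposure effect, so the plain reading is a level contrast.

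A reader might infer that the plan contains no possible slope term. The documents do not support that: length of hormonal use in Table 5 could act as one if it is updated over time, and the level formula above holds only when no such term is present. This limits the claim without closing the gap, because that covariate is not the named contrast.

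A reader might also infer that the slope test would be well powered. That holds only with long follow-up. Section 9.3 censors women who switch method types or become pregnant in the primary analysis, so short intervals are plausible and power could be low. The figure of 49 is also open to challenge, because section 7.2 describes the study population as women who have used contraception, although 8.1 lists never users.

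Finally, a slope contrast between self-chosen groups is itself open to confounding, as the last calculation shows. That stands and shapes the fix.

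**Conclusion.** The mismatch is real and should be fixed. The trend objective has no named trend contrast. Unless an exposure-by-time term is in the model, the stated coefficient mixes the starting gap with the slope difference. For 2010-2018 annual data, 0.5 points/yr shows as 2 points and an opposite 2-point gap hides it. That arithmetic rests only on balanced follow-up. All percentages are illustrations under assumed SDs, gaps and slopes, and they change greatly with follow-up length and comparator size.

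Two stronger conclusions do not follow. The exposure effect is not invalid in itself: with no gap and no slope difference it rejects at about 5%. Nor is the level contrast useless, because it fits the section 3.0 hypothesis. The point concerns one secondary objective and leaves the exacerbation analysis untouched.

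**What to change.** In 9.3, for the FEV1 trend objective:

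1. Include exposure, time and exposure x time in the GEE, and make exposure x time (difference in annual change, 95% CI) the trend estimate.
2. State the time scale for each group, including never users, who have no method start date.
3. Report the level difference separately, for the section 3.0 hypothesis.
4. Do not also enter time-updated length of hormonal use in this model, because it duplicates exposure x time.
5. Because groups are self-chosen, add time interactions for Table 5 covariates expected to affect decline, such as age and genotype class. Enter CFTR modulator use as time-varying; Table 5's own rationale for it is "Likely preserves pulmonary decline". Describe the slope contrast as open to confounding, since unmeasured traits would remain.
6. State one FEV1 scale: Table 5 uses liters and 9.3 uses ppFEV1.

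The cost is a revised paragraph and a little more modelling. Encounter dates and encounter-level FEV1 are already requested (Appendix III and IV), and the survey collects start and stop dates for modulators and dates or ages of use for contraceptives (Table 10). The downside is low precision for the slope where intervals are short or the non-hormonal group is small.

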9.1.3. Patient Surveys

Table 10: Information in online, self-respondent surveys

Survey O	nce Enrolled
• Demog	graphics: marital status, race/ethnicity, and education
	nedical history: ever smoked, ever had a blood clot requiring anticoagulation, # PICC lines placed, PORT in (dates)
Medic	ation history: ever taken CFTR modulator (with start and stop dates)
-	al history: Tubal ligation, hysteroscopic sterilization, hysterectomy, bilateral oophorectomy, other operation as made it impossible to get pregnant
• Menst	rual history: menarche, regularity of menstruation, menopause
• Contra	aception questionnaire
•	Questions regarding types of contraception used since 2008, start and stop dates of each method or age at first/last use. Questions are based off of the National Survey of Family Growth (NSFG)
• Pregna	ancy history questionnaire

- - Includes number of pregnancies in lifetime, year(s) pregnant, outcome of pregnancy, whether pregnancy was planned or not
 - Additional questions to include for funded study ([name] and [name]): times visited CF center during pregnancy and type of provider who cared for participant during pregnancy, ART

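### Section 9.3 promises a within-participant difference but names no within-woman estimator; a single GEE or Poisson exposure coefficient would mix between-woman and within-woman contrasts

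*Combined protocol and SAP*

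**What the plan says.** Section 9.3 names three models.

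- Lung function: "We will model ppFEV1 via generalized estimating equations (GEE), allowing for correlation within a subject, and compare via a fixed effect for exposure". The fixed effect is for exposure, not for the woman, and no working correlation structure is given.
- Exacerbations, the primary outcome: "We will use Poisson regression to calculate progestin-only and combined hormonal method to non-hormonal method pulmonary exacerbation rate ratios and 95% confidence intervals". No participant term, conditioning or clustering is mentioned.
- Respiratory microbiology: a GEE with a logit link.

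Directly after the ppFEV1 sentence comes the promise at issue, limited to women who change or stop a method: "we will estimate and compare within-participant difference in outcomes via the model (if numbers allow". Women who switch method type are censored in the primary analysis. Afterwards the team will "subsequently follow them to leverage within-patient data and analyze changes in pulmonary status and contraception".

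Measured confounding is handled by covariates: "See Table 5 for confounders and covariates that we will use to adjust for the primary and secondary outcomes". The survey (section 9.1.3, Table 10) asks for "start and stop dates of each method or age at first/last use", so before-and-after contrasts can be built.

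**The concern.** A population-averaged model with one exposure term does not separate two comparisons. One is a woman on a method against herself off it. The other is women who spend more time on a method against women who spend less. Allowing for within-subject correlation changes the weights and the standard errors, but it does not by itself make the coefficient a within-woman quantity. Restricting to women who change or stop reduces the mixing. It removes it only if all of them have the same share of exposed time.

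This matters because women choose their method (section 8.1), and the pulmonary covariates in Table 5 include neither baseline FEV1 nor prior exacerbation rate. Stable severity is therefore adjusted for only through proxies such as genotype class, BMI and CF-related diabetes. The within-participant analysis is the planned analysis best placed to remove stable differences between women. Without a named estimator, it could report a partly between-woman difference under a within-woman label. If healthier women spend more time on hormonal methods, the error would resemble the benefit hypothesised in section 3.0 for estrogen-containing methods. If sicker women do, it would run the other way.

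**Working it through.** The plan gives no figure for this analysis, so there is nothing to reproduce. The check asks what each candidate coefficient would show if the true effect were zero.

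**Inputs.** From the documents: nine calendar years, 2010 to 2018 (outcome follow-up starts in 2010 under section 9.3; section 5.0 gives 2018 or 2019 as the last year), and about half of women on hormonal methods (section 7.7). Assumed: correlation r = 0.15 to 0.30 between stable health and share of time exposed; ppFEV1 SD of 18 between women and 7 within; log exacerbation rate SD of 0.8; one change per woman, equally likely to leave 1 to 8 of the 9 years exposed. There is no covariate adjustment.

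**Step 1: share of exposure variance that lies between women.**
Var(share) = [(8² − 1)/12]/9² = 5.25/81 = 0.0648, so SD = 0.2546. Total exposure variance = 0.5 × 0.5 = 0.25. Between-woman fraction = 0.0648/0.25 = 0.259. An independence GEE therefore puts about 26% weight on the between-woman slope, even among switchers.

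**Step 2: ppFEV1, independence working correlation.**
Between-woman slope = r × 18/0.2546 = 10.6 (r = 0.15) or 21.2 (r = 0.30).
Bias = 0.259 × slope = 2.7 or 5.5 points.

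**Step 3: ppFEV1, exchangeable working correlation.**
The between part is shrunk by 7²/(7² + 9 × 18²) = 49/2965 = 0.0165.
Its weight becomes 0.0165 × 0.259/(0.741 + 0.0165 × 0.259) = 0.0057.
Bias = 0.0057 × slope = 0.06 or 0.12 points.

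**Step 4: exacerbations, plain Poisson (approximate).**
Log-rate shift = r × 0.2546 × 0.8/0.25 = 0.122 or 0.244. Rate ratio = exp(−0.122) = 0.88 or exp(−0.244) = 0.78.

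**Step 5: simulations in switchers with no true effect.** Run A: 300 switchers, 9 years, 60 data sets per setting, r = 0.15 and 0.30. Run B: the 40% of 575 women who switch, 9 records each, 0.8 exacerbations a year, 60 replicates.

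| Estimator | Run A, r = 0.15 | Run A, r = 0.30 | Run B |
|---|---|---|---|
| ppFEV1, independence GEE | +3.0 | +5.6 | +4.6 |
| ppFEV1, exchangeable GEE | +0.1 | +0.1 | +0.03 |
| ppFEV1, within-woman | 0.04 | 0.0 | −0.06 |
| Rate ratio, plain Poisson / independence | 0.88 | 0.79 | 0.77 |
| Rate ratio, exchangeable | not run | not run | 0.93 |
| Rate ratio, within-woman | 1.01 | 1.01 | 1.00 |

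A further run in switchers on its own assumed inputs gave +2.3 to +4.9 points for the independence GEE and rate ratios of 0.91 to 0.81 for plain Poisson. Its within-woman estimators gave about 0 and 1.0.

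**Step 6: scale.** Table 8 is built on a rate ratio of 0.70. On the log scale, ln 0.88/ln 0.70 = 0.36 and ln 0.77/ln 0.70 = 0.73. Even the exchangeable 0.93 gives ln 0.93/ln 0.70 = 0.20.

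**The case against.** The strongest reply is that the text leaves the analysis open and does not choose a wrong one. A reader might infer that section 9.3 makes the overall exposure coefficient the within-woman estimate, and so keeps confounding that the analysis is meant to remove. The documents do not support that reading. Saying that the difference will come from the model does not say which term will be reported, and a GEE with a person-mean term would also fit the words. The stated aim is to use within-patient data; removal of confounding is not mentioned.

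Other parts of the reply also stand.

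- The nearest antecedent of the model is the ppFEV1 GEE. Poisson regression appears earlier, for the between-group rate ratios, and is brought in only because the sentence speaks of outcomes in the plural.
- Allowing for within-subject correlation suggests a non-independence structure more naturally than independence. For ppFEV1 an exchangeable structure leaves almost no bias.
- The simulations omit the Table 5 covariates, which would absorb some of the difference between women.
- The confounder in the simulations is stable, so a fixed-effects estimator is bound to do well in them.
- The analysis is a follow-on, run only if numbers permit.

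What the reply does not answer is that no structure is named, no within-woman estimator is named, and exacerbations keep some bias even under an exchangeable structure (0.93 in Run B).

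**Conclusion.** The point holds as a gap in specification with a clear and inexpensive remedy. Section 9.3 promises a within-participant difference, and none of the models it names, taken with a single exposure coefficient, is a pure within-woman contrast when switchers differ in exposed time.

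The size depends on what is eventually fitted. For ppFEV1 it is about 0.1 point or less under an exchangeable GEE and about +2 to +6 points under independence. For exacerbations, a plain Poisson model gives spurious rate ratios of about 0.9 to 0.8. These figures show direction and range only. They rest on assumed correlations, SDs and switching patterns, without covariate adjustment, and their sign follows the assumption that healthier women spend more time on hormonal methods.

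The primary rate ratio is not affected, because women who switch are censored there.

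**What to change.** For women who change or stop a method, state in section 9.3:

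- Exacerbations: conditional fixed-effects Poisson, with follow-up time as the offset.
- ppFEV1: fixed-effects regression by woman, or the planned GEE with each woman's mean exposure added, reporting the within-woman term. Name the working correlation in either GEE.
- Both: age or calendar time, and time-varying covariates such as CFTR modulator use.
- A statement that time-varying confounding, for example switching prompted by a change in health, is not removed.

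The cost is SAP wording and standard Stata commands. No new data are needed, since exposure timing is already collected. Women with no exacerbations do not contribute to the conditional Poisson estimate, and women whose exposure does not change do not contribute to either within-woman estimate, so intervals will be wider.
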